| 10.2. Populations for Analyses..... | 33 |
| 10.2.1. Study Participant Disposition | 33 |
| 10.2.2. Study Participant Characteristics | 33 |
| 10.3. Statistical Analyses | 33 |
| 10.3.1. Pharmacokinetic Analyses..... | 33 |
| 10.3.1.1. Pharmacokinetic Parameter Estimation..... | 33 |
| 10.3.1.2. Pharmacokinetic Statistical Inference | 34 |
| 10.3.2. Safety Analyses..... | 34 |
| 10.3.2.1. Clinical Evaluation of Safety | 34 |
| 10.3.2.2. Statistical Evaluation of Safety | 34 |
| 10.3.3. Evaluation of Immunogenicity | 34 |
| 10.3.4. Interim Analyses | 34 |
| 11. References | 35 |

List of Tables

| Table | | Page |
|---------------|---|-------------|
| Table CGAY.1. | Objectives and Endpoints | 15 |
| Table CGAY.2. | Treatments Administered..... | 23 |
| Table CGAY.3. | Amendment Summary for Protocol I5Q-MC-CGAY Amendment(a)..... | 45 |

List of Appendices

| Appendix | | Page |
|-----------------|---|-------------|
| Appendix 1. | Abbreviations and Definitions | 36 |
| Appendix 2. | Clinical Laboratory Tests..... | 40 |
| Appendix 3. | Study Governance, Regulatory and Ethical Considerations | 41 |
| Appendix 4. | Blood Sampling Summary | 44 |
| Appendix 5. | Protocol Amendment I5Q-MC-CGAY(a) Summary A Randomized, Placebo-Controlled, Single-Dose Study to Assess the Pharmacokinetics, Safety, and Tolerability of Galcanezumab in Healthy Chinese Subjects | 45 |

1. Protocol Synopsis

Title of Study:

A Randomized, Placebo-Controlled, Single-Dose Study to Assess the Pharmacokinetics, Safety, and Tolerability of Galcanezumab in Healthy Chinese Subjects.

Rationale:

Galcanezumab is a humanized monoclonal antibody being developed for migraine prophylaxis. This is a study of galcanezumab in Chinese subjects and the results will be used to support registration for this indication in China.

Objective(s)/Endpoints:

| Objectives | Endpoints |
|--|--|
| 
Primary
 
To investigate the pharmacokinetics (PK) of galcanezumab following a single subcutaneous (SC) administration of galcanezumab to healthy Chinese subjects.
 | 
C_{max} and area under the concentration versus time curve from time zero to infinity ($AUC_{[0-\infty]}$) of galcanezumab.
 |
| 
Secondary
 
To investigate the safety and tolerability of a single SC administration of galcanezumab to healthy Chinese subjects.
 | 
Incidence of adverse events (AEs) and serious AEs.
 |

Summary of Study Design:

Study I5Q-MC-CGAY is a single-center, randomized, subject- and investigator-blind, placebo-controlled, parallel-group, single-dose study in healthy Chinese subjects. Healthy males and females, as determined by medical history, physical examination, vital signs, clinical laboratory tests, and electrocardiograms, will be enrolled. Subjects are to be native Chinese, at least 18 years of age, with a body mass index between 18.5 and 35.0 kg/m², inclusive, at screening. Females must test negative for pregnancy and females of childbearing potential must agree to use a reliable method of contraception during the study and for 5 months after dosing. Subjects will be excluded if they have allergies to either monoclonal antibodies, diphenhydramine, epinephrine, or methylprednisolone.

Treatment Arms and Planned Duration for an Individual Subject:

Each subject will have a screening visit within 28 days prior to dosing. Subjects will be randomized within a cohort to receive galcanezumab or placebo. Subjects in Cohort A will receive a single dose of 120 mg galcanezumab or placebo; Cohort B will receive a single dose of 240 mg galcanezumab or placebo. Dosing of cohorts may be conducted in parallel or sequentially at the discretion of the Investigator.

Subjects will be admitted to the clinical research unit on Day -1 and may be discharged after all assessments have been completed on Day 3. Subjects may remain inpatient up to Day 15 to improve visit compliance, at the discretion of the investigator. A single SC dose of galcanezumab or placebo will be administered according to

randomization on the morning of Day 1. Subjects will return for outpatient visits for up to 5 months after dosing for safety, tolerability, immunogenicity, and PK assessments.

Number of Subjects:

Approximately 30 subjects may be enrolled in this study to adjust for any discontinuations and try to ensure that approximately 20 subjects complete the study (10 per cohort; 8 galcanezumab and 2 placebo). The sample size is customary for Phase 1 studies evaluating safety, tolerability, and PK, and is not powered on the basis of statistical hypothesis testing.

Statistical Analysis:

There will be no formal statistical analyses. The PK, safety, tolerability, and immunogenicity data will be summarized using standard descriptive statistics, as appropriate.

2. Schedule of Activities

Study Schedule Protocol I5Q-MC-CGAY

| Week | | | 0 | | | | | 1 | | | 2 | 3 | 4 | 6 | 8 | 10 | 12 | 16 | 20 | |
|--|------------------|----------------|----------------|----|----|----|-----|-----|-----|-----|-----|-----|-----|------|------|------|------|------|------------------|---|
| Day ^a | SCR ^b | - 1 | 1 | 2 | 3 | 5 | 6 | 8 | 10 | 12 | 15 | 22 | 29 | 43 | 57 | 71 | 85 | 113 | 141 ^c | |
| Visit Window (days) | | | | | | | | | | | ±1 | ±2 | ±2 | ±3 | ±3 | ±3 | ±3 | ±3 | ±3 | |
| CRU admission/visits ^d | X | Inpatient stay | | | | | X | X | X | X | X | X | X | X | X | X | X | X | X | X |
| Randomization | | | X | | | | | | | | | | | | | | | | | |
| Study drug injection | | | X ^e | | | | | | | | | | | | | | | | | |
| Informed Consent | X | | | | | | | | | | | | | | | | | | | |
| Eligibility assessment | X | | | | | | | | | | | | | | | | | | | |
| Medical history | X | | | | | | | | | | | | | | | | | | | |
| Recording of AEs ^f | X | X | X | X | X | X | X | X | X | X | X | X | X | X | X | X | X | X | X | |
| Concomitant medication | X | X | X | X | X | X | X | X | X | X | X | X | X | X | X | X | X | X | X | |
| Physical exam ^g | X | X | Predose | | X | | | X | | | X | | X | X | X | | X | X | | |
| Body temperature | X | | | | | | | | | | | | | | | | | | | |
| Height, weight ^h | X | | Predose | | | | | | | | | | | | | | | | X | |
| Vital signs (hours) ⁱ | X | | Predose, 8 | 24 | X | X | X | X | X | X | X | X | X | X | X | X | X | X | X | |
| Single 12-lead ECG (hours) | X | X | | 24 | | | | | | | | | | | | | | X | X (ED only) | |
| Clinical Laboratory tests | X | X | Predose | | | | | | | | X | | | | X | | | X | X (ED only) | |
| Serology: HIV, HBV, HCV | X | | | | | | | | | | | | | | | | | | | |
| Urine drug screen, ethanol breath test ^j | X | X | | | | | | | | | | | | | | | | | | |
| Chest x-ray and T-SPOT test | X | | | | | | | | | | | | | | | | | | | |
| Pregnancy test ^k | X | X | | | | | | | | | | | | | | | | | X | |
| Galcanezumab PK blood sampling (hours) ^l | | | 8 | 24 | 48 | 96 | 120 | 168 | 216 | 264 | 336 | 504 | 672 | 1008 | 1344 | 1680 | 2016 | 2688 | 3360 | |
| PGx blood sampling | | | Predose | | | | | | | | | | | | | | | | | |
| Immunogenicity blood sampling ^m | | | Predose | | | | | | | | X | | X | | X | | X | | X | |

Abbreviations: AE = adverse event; CRU = clinical research unit; ECG = electrocardiogram; ED = early discontinuation; HBV = hepatitis B virus; HCV = hepatitis C virus; HIV = human immunodeficiency virus; PK = pharmacokinetics; PGx = pharmacogenetics; SCR = screening; T-SPOT = T-SPOT® tuberculosis test.

- a If these procedures cannot be done on the same day, they should be done at closest time possible.
- b Screening evaluations to be performed within 28 days prior to dosing.
- c Also procedures for early discontinuation.
- d Subjects will be admitted to the CRU on Day -1, and may be discharged on Day 3 after the procedures scheduled at 48 hours after dosing have been completed. Subjects may remain inpatient up to Day 15 to improve visit compliance, at the discretion of the investigator. Unless specified, safety monitoring procedures should be done close to the dosing time on Day 1, except for screening and the day before dosing.
- e Per randomization scheme. Where possible, subjects to stay in the semi-recumbent position for 4 hours following study drug administration.
- f The investigator will record additional details regarding AEs related to injection sites and hypersensitivity events.
- g Complete physical examination to be performed at screening and at the final visit for each subject; symptom-directed physical examination only at other visits and as clinically indicated.
- h Height to be measured at screening only.
- i Vital signs include sitting blood pressure and pulse rate.
- j Additional urine drug screen and breath ethanol tests may be performed at the investigator's discretion.
- k Females only. Blood pregnancy test will be done on screening; urine test at other times as indicated, or when performed at the investigator's discretion.
- l It is preferred that on days without dosing the PK samples should be taken close to the Day 1 dosing time. Nominal PK sampling times are given as targets to be achieved within reasonable limits. Additional samples may be taken (see Section 9.6.1).
- m Additional samples may be taken (see Section 9.6.1).

3. Introduction

3.1. Study Rationale

This is a study of galcanezumab in Chinese subjects. The main purpose of this study is to evaluate the pharmacokinetics (PK), safety, and tolerability of galcanezumab in healthy Chinese subjects. The results from this study will be used to support registration for migraine prophylaxis in China.

3.2. Background

Galcanezumab (LY2951742) is a humanized monoclonal antibody that binds to calcitonin gene-related peptide (CGRP), a peptide that is widely expressed in the central and peripheral nervous system and acts as a local facilitator of inflammatory processes. Lilly is currently evaluating galcanezumab for the prophylaxis of migraine and cluster headache.

3.2.1. Clinical Experience with Galcanezumab

Four clinical pharmacology studies with galcanezumab have been completed to date in healthy subjects. The subject population included 446 healthy subjects of whom 419 subjects received at least 1 dose of galcanezumab (dose range 1 to 600 mg).

Two Phase 2 studies and the double-blinded phase of three Phase 3 studies in migraine patients have completed, and demonstrated consistent efficacy in migraine prevention. The treatment phase of a further Phase 3 open-label study in migraine patients has also completed. Additional Phase 3 studies in migraine patients are ongoing, including 2 studies conducted in Japanese patients. In the completed Phase 2 studies, a total of 380 migraine patients received repeated doses of galcanezumab; 150 mg every 2 weeks in 1 study, or 5 to 300 mg every 4 weeks in the other. In the completed Phase 3 studies, safety and efficacy of galcanezumab were tested in migraine patients who received either placebo or galcanezumab at doses of 120 mg monthly, after a 240 mg loading dose, or 240 mg monthly. Safety and efficacy profiles of both doses were comparable.

In September 2018, galcanezumab (Emgality™) was approved in the US for the prevention of migraine in adults. Additionally, galcanezumab was approved in the EU in November 2018, for the prophylaxis of migraine in adults who have at least 4 migraine days per month. The approved dose of galcanezumab is a loading dose of 240 mg followed by monthly doses of 120 mg.

In addition to migraine prevention, safety and efficacy of galcanezumab were also tested in 2 completed Phase 3 studies in patients with episodic and chronic cluster headache at 300 mg monthly dose.

3.2.1.1. Clinical Pharmacokinetic Data

Galcanezumab exhibited PK properties consistent with an immunoglobulin G monoclonal antibody. Based on population PK analysis, the apparent clearance of galcanezumab was approximately 0.008 L/h (34% inter-individual variability), the half-life associated with the terminal elimination phase ($t_{1/2}$) was 27 days and the mean maximum observed drug

concentration (C_{max}) is expected to be achieved by 5 to 7 days after subcutaneous administration. Galcanezumab exposure increases proportionally with dose. Race is not a statistically significant covariate of galcanezumab PK.

3.2.1.2. Clinical Safety Data

Two serious adverse events (SAEs) were reported in subjects who received galcanezumab during the clinical pharmacology program: a death due to drowning, which was not considered by the investigator to be related to investigational product and atrial fibrillation, which was considered to be possibly related to investigational product. Other than the subject who died, no subjects discontinued from any clinical pharmacology study because of an adverse event (AE).

In the clinical pharmacology program, the incidences of common treatment-emergent adverse events (TEAEs), including headache, injection site erythema, injection site pain, and upper respiratory tract infection, were similar to those of subjects who received at least 1 dose of placebo, and frequency did not appear dose dependent. A low frequency (1%) of TEAEs related to cardiovascular safety occurred in subjects who received at least 1 dose of galcanezumab, and none occurred in subjects who received placebo. No consistent blood pressure, heart rate, or electrocardiogram (ECG) findings were observed across treatment groups, including placebo. There were no reports of TEAEs related to suicidal ideation and behavior.

In an integrated analysis of data from all 6 ongoing or completed migraine patient studies, 67.0% of patients in the galcanezumab-pooled dose group reported at least one TEAE. The common TEAEs (reported by $\geq 1.5\%$ of patients before rounding) in this group included injection site pain, nasopharyngitis, upper respiratory tract infection, and injection site reaction (ISR). A total of 81 patients (3.1%) in the galcanezumab-pooled dose group discontinued due to AEs. Those AEs that led to discontinuation in >2 patients in this group were: ISR, migraine, urticaria, injection site erythema, and rash. Serious hypersensitivity cases of urticaria have been reported in migraine patients receiving galcanezumab; non-serious adverse drug reactions included ISR, vertigo, constipation, and pruritus.

Nine of 160 subjects developed treatment-emergent antidrug antibody after a single dose of 240 mg galcanezumab solution in a clinical pharmacology study. Overall, the presence of antidrug antibodies (ADAs) did not affect the PK, efficacy, or safety of galcanezumab. Aggregate findings from healthy subjects and patients who developed treatment-emergent ADA did not reveal a relationship between injection site reactions or hypersensitivity reactions and immunogenicity

More information about the known and expected benefits, risks and reasonably anticipated AEs may be found in the Investigator's Brochure (IB). Information on AEs expected to be related to the investigational product may be found in Section 7 (Development Core Safety Information) of the IB.

3.3. Benefit/Risk Assessment

This study will evaluate single doses of 120 and 240 mg galcanezumab. The justification of these doses can be found in Section 5.5. No clinically significant safety or tolerability concerns

have been identified in subjects to date for galcanezumab up to the highest single dose given (600 mg). In this study, there is no anticipated therapeutic benefit for the subjects. Potential risks include but are not limited to hypersensitivity reactions. The risk profile of galcanezumab remains supportive of further clinical development.

More information about the known and expected benefits, risks, SAEs and reasonably anticipated AEs of galcanezumab are to be found in the IB.

4. Objectives and Endpoints

Table CGAY.1 shows the objectives and endpoints of the study.

Table CGAY.1. Objectives and Endpoints

| Objectives | Endpoints |
|--|---|
| Primary To investigate the PK of galcanezumab following a single SC administration of galcanezumab to healthy Chinese subjects. | C_{max} and area under the concentration versus time curve from time zero to infinity ($AUC_{[0-\infty]}$) of galcanezumab. |
| Secondary To investigate the safety and tolerability of a single SC administration of galcanezumab to healthy Chinese subjects. | Incidence of AEs and SAEs. |
| Exploratory To evaluate galcanezumab with respect to immunogenicity in healthy Chinese subjects. | Development of ADAs to galcanezumab. |

5. Study Design

5.1. Overall Design

This is a Phase 1, single-center, randomized, subject- and investigator-blind, placebo-controlled, parallel-group, single-dose study in healthy Chinese subjects. Subjects will be assigned to 1 of 2 cohorts and randomized to receive galcanezumab or placebo (4:1 ratio), as described in Section 7.2. Subjects will receive the following treatments:

- Cohort A: a single dose of 120 mg galcanezumab or placebo
- Cohort B: a single dose of 240 mg galcanezumab or placebo

Dosing of cohorts may be conducted in parallel or sequentially at the discretion of the Investigator.

Subjects will be admitted to the clinical research unit (CRU) on Day -1 and may be discharged after all assessments have been completed on Day 3. Subjects may remain inpatient up to Day 15 to improve visit compliance, at the discretion of the investigator. A single SC dose of galcanezumab or placebo will be administered according to randomization on the morning of Day 1. Subjects will return for outpatient visits for up to 5 months after dosing for safety, tolerability, immunogenicity, and PK assessments.

Safety and tolerability will be assessed throughout the study by means of vital sign measurements, clinical laboratory tests, ECG, physical examinations (as indicated), and AE recording.

Study governance considerations are described in detail in [Appendix 3](#).

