5.2. Number of Participants

Approximately 30 subjects may be enrolled to ensure that approximately 20 subjects complete the study. Up to 15 subjects will be enrolled in each of 2 cohorts and randomized to receive either galcanezumab or placebo (4:1 ratio), to ensure that approximately 8 subjects receiving galcanezumab and 2 subjects receiving placebo complete each cohort. For purposes of this study, a subject will be considered to have completed the study when they complete the follow-up procedures at approximately 20 weeks, as shown in the Schedule of Activities (Section 2).

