5.4. Scientific Rationale for Study Design

The subject- and investigator-blinded, randomized, placebo-controlled design minimizes bias on safety and tolerability assessments, and allows a more robust comparison among galcanezumab and placebo doses.

The selection of healthy subjects is appropriate and in keeping with standard regional practices for clinical pharmacology studies. The inclusion and exclusion criteria are chosen to select subjects who are known to be free from any significant illness and from any condition that could affect their safety or interfere with meeting the study objectives.

The approximately 20-week PK sampling is based on clinical PK data for galcanezumab following administration of single doses of up to 600-mg to healthy subjects ($t_{1/2}$ was 27 days). Based upon the available clinical PK data for galcanezumab, the duration of this study is adequate to achieve the study objectives.

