7.2. Method of Treatment Assignment

Subjects who meet the study entry criteria will be randomized to receive either galcanezumab or placebo in a 4:1 ratio via a computer-generated random sequence using an interactive web-response system (IWRS).

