7.2.1. Selection and Timing of Doses

Doses will be administered according to randomization on the morning of Day 1. The actual time of all dose administrations will be recorded in the subject's electronic case report form (eCRF).

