9.3. Treatment of Overdose

For the purposes of this study, an overdose of galcanezumab is considered any dose higher than the dose assigned through randomization. There is no specific antidote for galcanezumab. In case of known or suspected overdose, it is recommended that the subject be monitored for any signs or symptoms of adverse reactions and appropriate symptomatic treatment be instituted immediately.

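### Protocol 7.2 does not say how a subject is placed in the 120 mg or 240 mg cohort, so randomization to dose level is not assured, and the SAP's single placebo group appears to mix both cohorts

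*Protocol*

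**What the plan says.** - Protocol 5.1: "Subjects will be assigned to 1 of 2 cohorts and randomized to receive galcanezumab or placebo (4:1 ratio", with the method said to be in 7.2. SAP 5 repeats this.
- Protocol 7.2: "Subjects who meet the study entry criteria will be randomized to receive either galcanezumab or placebo in a 4:1 ratio", by a computer-generated sequence in the IWRS. It mentions neither cohort, dose level nor stratification.
- Protocol Synopsis: "Subjects will be randomized within a cohort to receive galcanezumab or placebo". On timing: "Dosing of cohorts may be conducted in parallel or sequentially at the discretion of the Investigator".
- Protocol 5.2 gives cohort size only: "Up to 15 subjects will be enrolled in each of 2 cohorts and randomized to receive either galcanezumab or placebo (4:1 ratio".
- Protocol 5.4 credits the design with giving what "allows a more robust comparison among galcanezumab and placebo doses".
- Protocol 7.1, Table CGAY.2: placebo is one 1 mL injection in Cohort A and two in Cohort B, the same as active drug in that cohort.
- SAP 6 lists three treatments for the tables: Placebo, 120 mg and 240 mg. SAP 9.4.1 and 9.4.6 summarize adverse events and injection-site reactions by treatment. SAP 3 says the table shells are a separate document.
- Protocol 10.3 and SAP 8 base safety on all enrolled subjects. SAP 9.4.9 plans no inference.
- SAP 9.3.1 allows an alternative AUC for assessing exposure between dose groups if AUC(0-∞) cannot be obtained for everyone.

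**The concern.** Section 5.1 uses one verb for entering a cohort and another for receiving drug or placebo, and its cross-reference supplies a method only for the second. A site could not tell from these documents how the next eligible subject comes to be in the 120 mg or the 240 mg cohort. Enrolment order, calendar time or investigator choice would all fit the text.

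The scope for the cohorts to differ is not negligible. Protocol 6.1 sets no upper age limit and admits BMI from 18.5 to 35.0 kg/m², Protocol 5.1 leaves an inpatient stay to Day 15 to discretion, and one versus two injections makes the cohort visible to staff.

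At stake are the descriptive safety tables for the secondary endpoint. The randomization as described protects drug against placebo within each cohort. A table with one placebo column shows something else: each dose beside a placebo group drawn from both cohorts. Any comparison of 240 mg with 120 mg, including the exposure assessment in SAP 9.3.1, rests entirely on how cohorts were filled.

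**Working it through.** **1. The plan's own counts (Protocol 5.2 and 10.1).** Completers per cohort: 10 × 4/5 = 8 galcanezumab and 10 × 1/5 = 2 placebo; two cohorts give 20. Enrolled per cohort: 15 × 4/5 = 12 and 15 × 1/5 = 3; two cohorts give 30. Both stated totals reproduce.

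**2. Make-up of one pooled placebo group.** 3 + 3 = 6 enrolled, or 2 + 2 = 4 completers. For either dose, half (3 of 6, or 2 of 4) comes from the other cohort.

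**3. Effect of a cohort difference.** Let pA and pB be the background adverse-event rates in the two cohorts and d = pB − pA. With equal placebo numbers the pooled placebo rate is (pA + pB)/2.
- 120 mg minus pooled placebo = drug effect + pA − (pA + pB)/2 = drug effect − d/2.
- 240 mg minus pooled placebo = drug effect + d/2.
- 240 mg minus 120 mg = difference in drug effects + d.
- Own-cohort comparison: shift 0.
- All galcanezumab minus pooled placebo: shift 0, because 4:1 in each cohort gives both groups the same cohort mix.

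The documents give no value for d. Assumed range, in percentage points:
- d = 10: per-dose shifts −5 and +5; between doses 10.
- d = 20: −10 and +10; between doses 20.
- d = 30: −15 and +15; between doses 30.

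The same algebra applies to exposure: a cohort difference in background exposure enters the between-dose assessment in full.

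**4. Set against sampling error.** SE = √[p(1−p)(1/n₁ + 1/n₂)], with an assumed p = 0.30, so p(1−p) = 0.21.
- Pooled placebo, 12 v 6: √(0.21 × 0.250) = 0.229. 8 v 4: √(0.21 × 0.375) = 0.281.
- Own-cohort placebo, 12 v 3: √(0.21 × 0.417) = 0.296. 8 v 2: √(0.21 × 0.625) = 0.362.

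The per-dose shift of 5 to 15 points is smaller than the SE of 23 to 28 points. Using only own-cohort placebo avoids the shift but raises the SE to 30 to 36 points.

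**5. One versus two injections.** With an assumed reaction risk q per injection, independent between injections, placebo incidence is q in Cohort A and 1 − (1−q)² in Cohort B. The difference is q(1−q), and the pooled rate is off by half of it for each dose.
- q = 0.05: difference 0.048, half 0.024.
- q = 0.10: 0.090, half 0.045.
- q = 0.20: 0.160, half 0.080.

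Pooled placebo is therefore about 2 to 8 points too high as a comparator for 120 mg and too low for 240 mg. This needs no selection, and randomizing dose level would not remove it.

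**6. Four-arm allocation at the planned size.** 30 × (4, 1, 4, 1)/10 = 12, 3, 12, 3, which are the enrolled numbers from step 1. Each block of 10 holds all four arms, so every arm has the same expected mix of early and late subjects and the expected d is 0.

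**The case against.** A reader might infer two stronger things, and the documents support neither.

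First, that the protocol contradicts itself. Section 9.3 says "an overdose of galcanezumab is considered any dose higher than the dose assigned through randomization", and 7.2.1 says "Doses will be administered according to randomization on the morning of Day 1". Both are compatible with within-cohort randomization: in Cohort A it yields 120 mg or placebo, in Cohort B 240 mg or placebo. The wording of 9.3 is loose and could suggest that dose level is randomized, but tidying it is editorial.

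Second, that the comparisons are not randomized. Silence about a method is not evidence of a non-random one. Under parallel dosing the IWRS could place subjects at random, and footnote e to the Schedule of Activities cites a randomization scheme that is not among these documents. The supportable statement is that randomization to dose level is not assured.

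On consequence the opposing case is strong. The study is descriptive, with one center and one set of criteria. The size of d is assumed, and the resulting per-dose shift is below the sampling error and below one event among six placebo subjects (1/6, or 17 points). No dose-minus-placebo safety estimate is defined. Adverse events and injection-site reactions are also listed by subject. The table shells might already split placebo by cohort.

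These points limit the weight of the concern. They do not supply the missing method or make a pooled one- and two-injection placebo rate a match for either dose. In a study this small, readers compare table columns by eye, so how the columns are built matters.

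**Conclusion.** The point holds in a limited form. Neither document says how subjects are placed in a cohort, and the section cited for it does not supply the method, so randomization to dose level is not assured. With one pooled placebo group, a cohort difference d would shift the per-dose adverse-event differences by d/2 in opposite directions, and 240 versus 120 mg by d. That is 5 to 15 and 10 to 30 points under an assumed d of 10 to 30 points. Selection is possible and is not shown.

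Separately, a pooled placebo injection-site rate would be about 2 to 8 points off for each dose, at an assumed 5 to 20% independent risk per injection.

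Pooling itself is inferred from the treatment list in SAP 6. Within-cohort comparisons and all galcanezumab versus pooled placebo are free of the cohort shift, and the primary per-dose PK summaries are unaffected. This is an inexpensive improvement to a descriptive study and puts no planned inference in doubt.

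**What to change.** 1. **Protocol 7.2 (and 5.1).** If cohorts are dosed in parallel, have the IWRS randomize each subject across four arms, 120 mg : one-injection placebo : 240 mg : two-injection placebo, at 4:1:4:1 (12:3:12:3 of 30 enrolled). If dosing is sequential, state that cohorts fill in enrolment order, and that between-dose comparisons and each dose against pooled placebo are not randomized; qualify 5.4 to match.
2. **SAP 9.4.6.** Under either option, show placebo by cohort (one versus two injections) as well as pooled in the injection-site table. Under sequential dosing, do the same in the adverse-event table of SAP 9.4.1.
3. **Editorial.** Align the wording of Protocol 9.3 with 7.2.

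Cost: a different IWRS list, a few sentences and extra columns in one or two tables. Sample size and doses do not change. Syringes come in single-syringe cartons (Protocol 7.1.1), so repackaging should not be needed. There are two drawbacks. Four-arm randomization needs both cohorts open together, and placebo columns by cohort hold only 2 or 3 subjects each, so they should sit beside the pooled column and not replace it.
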